9.3.3 Hearing Aids and Glasses

For the purposes of this study, subjects have the option to use their own hearing aids if they are appropriately fit. If a subject does not have appropriately fit hearing aids they will be provided prior to any study related assessments. Impressions will be taken and earmolds provided if needed. The decision to replace hearing aids will be based on the clinical judgement of the investigator with verification of such recorded on a study Case Report Form.

Subjects are required to have a minimum corrected near vision acuity of 20/40 as measured on a Near Vision Screening test. If a subject does not meet this criteria and does not have appropriately fit glasses, they will be withdrawn from the study.

9.3.4 Preoperative Visit 1 (POV1) - Screening

Participants are consented into the study. Eligibility for the study will be confirmed. During this preoperative screening visit, each participant will be randomized in a 1:1 ratio to either the immediate CI (Arm A) or hearing aid (delayed CI Arm B). During POV1, both Arm A and Arm B subjects will complete the neuropsychological assessments as described in Section 9.2.1 with appropriately fitted hearing aids and glasses (if required).

9.3.5 Preoperative Visit 2 (POV2) - Baseline

Preoperative visit 2 (POV2) baseline will occur 4-6 weeks post POV1 (+/- 2 weeks) to enable scheduling of surgery for Arm A subjects. Both Arm A and Arm B subjects will complete POV2 with appropriately fit hearing aids and glasses (if required). The full neuropsychological battery in addition to the audiology, psychosocial, physical, and quality of life metrics will be completed as described in Section 9.2. Speech recognition will be assessed in the everyday listening condition (aided bilaterally) and the ear to be implanted listening conditions with the contralateral ear plugged. Datalogs will be retrieved for the hearing aid.

Medical history will be completed minimally via the ACE 27 index. The Investigator or appropriately delegated staff may add additional otologic history (hearing history) which they deem relevant to the study.

9.3.6 Surgery – Arm A

Arm A subjects will be implanted with the Cochlear Nucleus® Profile™ Slim Modiolar (532) cochlear implant or the Cochlear Nucleus CI632 cochlear implant 1 week (+/- 1 week) post POV2.

An intraoperative X-ray will be obtained (preferably a lateral or modified Stenver's view) following the placement of the electrode and prior to closing.

9.3.7 Imaging

Following surgery, subjects will undergo a Computed Tomography (CT) scan according to the specifications provided by the study sponsor. Retrospective analysis of the CT scan will be done via reconstruction to determine electrode position and distance to the modiolus by an independent centralized imaging review center and a de-identified report will be sent to the sponsor in line with HIPAA Standards.

9.3.8 Clinical Review Visits (CRV)

9.3.8.1 CI review – Arm A

CI activation will occur in the standard clinical manner at each field site at approximately two weeks post-surgery (+/- 3 weeks). Four to six clinical review visits will be scheduled at each field site between activation and FUV1, six (6) months from POV2. These visits can contain device adjustments as well as counselling on hearing and listening strategies, and discussion of hearing assistive technology.

We propose the following topics are discussed during the six months of cochlear implant use:

- Hearing assistive technology
- Communication strategies
- Listening in noise
- Understanding hearing loss

Needs for various hearing assistive technologies (HATs) will be assessed and, if the audiologist deems that it is appropriate, recommendations will be made.

Following each CI mapping appointment an anonymized .cdx file labelled with the Subject ID will be provided to the study sponsor in order to evaluate program settings and usage data.

9.3.8.1.1 Audibility Review – three months post POV2.

As part of a clinical review visit, at three (3) months (+/- 4 weeks) post POV2, audibility will be assessed:

- Implanted ear only: Aided speech recognition with CNC words at 60 dBA (2 lists)
- Everyday listening condition (bimodal): Sound field thresholds at 500, 1000, 2000, 4000 Hz

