9.3.8.2 Hearing aid review – Arm B

Over the course of the hearing aid intervention, the subjects will be followed for hearing aid checks including verification of fitting, be counselled on hearing and listening strategies, and discuss hearing

assistive technology. Four to six clinical review visits will be scheduled at each field site between FUV1 and six (6) months from POV2.

We propose the following topics are discussed during the six months of the hearing aid intervention:

- Hearing assistive technology
- Communication strategies
- Listening in noise
- Understanding hearing loss

Needs for various hearing assistive technologies (HATs) will be assessed and, if the audiologist deems that it is appropriate, recommendations will be made.

Following each hearing aid fitting and follow up session an anonymized program settings file will be provided to the study sponsor in order to evaluate program settings and usage data.

9.3.8.2.1 Audibility Review – three months post POV2.

As part of the clinical review visits, at three (3) months (+/- 4 weeks) post POV2, audibility will be assessed.

- Implanted ear only: Aided speech recognition with CNC words at 60 dBA (2 lists)
- Everyday listening condition (bilateral hearing aids): Sound field thresholds at 500, 1000, 2000, 4000 Hz

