9.3.10 Surgery – Arm B

Arm B subjects will be implanted with the Cochlear Nucleus® Profile™ Slim Modiolar (532) cochlear implant or the Cochlear Nucleus CI632 cochlear implant 1 week (+/- 1 week) post FUV1.

An intraoperative X-ray will be obtained (preferably a lateral or modified Stenver's view) following the placement of the electrode and prior to closing.

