6.1.2 Visit Windows

Unless otherwise specified, visit assessments will be analyzed for each analysis time point as described in Sections 6.6 and 6.7.

Each test measure by arm/visit abbreviation is described in the table below.

Where:

A = Arm A, B = Arm B, and x = number of months post-baseline measure.

[figure not shown]
Procedure	Screening POV1	Baseline POV2	FUV1	FUV2	FUV3
HI-MoCA	A0 or B0		A6 or B6	A12 or B12	B18
HHIE-S	A0 or B0		A6 or B6	A12 or B12	B18
Cogstate		A0 or B0	A6 or B6	A12 or B12	B18
SSQ12		A0 or B0	A6 or B6	A12 or B12	B18
UCLA		A0 or B0	A6 or B6	A12 or B12	B18
GDS		A0 or B0	A6 or B6	A12 or B12	B18
LAQ		A0 or B0	A6 or B6	A12 or B12	B18
HUI-III		A0 or B0	A6 or B6	A12 or B12	B18
CNC words		A0 or B0	A6 or B6	A12 or B12	B18
AzBio sentences		A0 or B0	A6 or B6	A12 or B12	B18
Audiometric thresholds	A0 or B0		A6 or B6	A12 or B12	B18

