6.4 Handling of Missing Data

All attempts will be made to limit the amount of missing data. Unless otherwise specified, missing data will be handled by multiple imputation for the primary endpoint (SSQ12) with covariates of gender, age and baseline in the ITT Analyses. For all other analyses, no attempt will be made to impute missing data, and the number of observations available will be reported so the reader can assess the impact of missing data.

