6.7.1.1 Secondary Analyses

All secondary analyses will be presented using descriptive statistics and analyzed using pairwise correlations to compare the mean score of the cochlear implant Arm A to that of the hearing aid control Arm B. The familywise error rate in the secondary analyses will be controlled by a Bonferroni correction using a significance level of $p = 0.01$.

Investigating treatment effect on:

- Psychosocial measures:
 - UCLA loneliness Scale:
 - ☒ A6 vs B6
 - Geriatric Depression Scale (GDS):
 - ☒ A6 vs B6
- Audiologic measures:
 - CNC words:
 - ☒ A6 vs B6
 - AzBio Sentences:

Statistical Analysis Plan		Page 12 of 16
Sponsor Cochlear	Study Hearing Loss in Older Adults	CIP Version 9.0

☒ A6 vs B6

- Quality of life:
 - Health Utilities Index Mark III (HUI-III):
 - ☒ A6 vs B6

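### Single-ear CNC words are scored at three months in both arms but used in no SAP analysis, so the early result of anyone lost before FUV1 is discarded

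*Protocol*

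**What the plan says.** Protocol 9.3.8.1.1 (Arm A) lists, at three months after POV2, "Implanted ear only: Aided speech recognition with CNC words at 60 dBA (2 lists"). Protocol 9.3.8.2.1 sets the same test for Arm B: "As part of the clinical review visits, at three (3) months (+/- 4 weeks) post POV2, audibility will be assessed". The schedule in Protocol section 5 agrees: the single-ear CNC row has a three-month mark under the clinical review visits of both arms, and the everyday-listening row has none. Arm B surgery comes "1 week (+/- 1 week) post FUV1" (Protocol 9.3.10), so Arm B's three-month score is a hearing-aid score.

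SAP 6.1.2 states "Each test measure by arm/visit abbreviation is described in the table below" and defines the labels as "A = Arm A, B = Arm B, and x = number of months post-baseline measure". CNC words appear there at months 0, 6, 12 and 18 only. The CNC comparison in SAP 6.7.1.1 is A6 vs B6, "analyzed using pairwise correlations to compare the mean score of the cochlear implant Arm A to that of the hearing aid control Arm B". It is one of five measures tested at 0.01. The tertiary CNC contrasts in 6.7.1.2 use the same months.

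On missing data, SAP 6.4 says "missing data will be handled by multiple imputation for the primary endpoint (SSQ12) with covariates of gender, age and baseline in the ITT Analyses", and then "For all other analyses, no attempt will be made to impute missing data". SAP 4.1 allows for 20% attrition without replacement and does not say by which visit.

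**The concern.** The three-month CNC test is the only scheduled speech outcome between baseline and FUV1. For a subject who leaves between month 3 and FUV1 it is the latest speech score on file, and for single-ear CNC it is the same test in the same ear. The SAP reads it nowhere. The subject is dropped from the CNC comparison, and the SSQ12 imputation cannot tell someone who was doing well at month 3 from someone who was doing badly.

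The available-case CNC comparison is unbiased only if missingness is unrelated to early performance. The trial is unblinded (SAP 4.2) and the arms wait for different things, so that cannot be taken for granted. Even when it holds, information already collected from patients is thrown away.

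**Working it through.** **1. The plan's own figure.** SAP 5.1.1 gives a mean change of 3.0 with SD 1.8, so d = 3.0/1.8 = 1.667. With a two-sample t-test at two-sided 0.025, power is 0.784 with 8 per arm and 0.844 with 9. Then 9/0.8 = 11.25, rounded up to the SAP's 12 per arm. With 30 randomised per arm and 20% lost, 24 remain and power is 0.9996. Primary power is therefore not at stake.

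**2. Who is affected.** 60 × 0.20 = 12 subjects, 6 per arm, if all the allowed attrition falls before FUV1. Only those lost after month 3 have the unused score. The documents do not give that share.

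**3. Random dropout: precision.** Let ρ be the correlation of month-3 with FUV1 CNC (not in the documents; 0.7 to 0.9 assumed), n_obs = 24 the number per arm seen at FUV1, and n_aux the number with a month-3 score. The variance of an arm mean that uses the score is σ²[(1 − ρ²)/n_obs + ρ²/n_aux], against σ²/n_obs without it. The ratio is 1 − ρ²(1 − n_obs/n_aux).

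| Losses after month 3 | n_aux | Ratio, ρ = 0.7 | Ratio, ρ = 0.9 |
|---|---|---|---|
| All | 30 | 1 − 0.49 × 0.200 = 0.902 | 1 − 0.81 × 0.200 = 0.838 |
| Half | 27 | 1 − 0.49 × 0.111 = 0.946 | 1 − 0.81 × 0.111 = 0.910 |

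Variance falls by about 10 to 16% in the first case and 5 to 9% in the second. There is no bias in either.

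**4. Informative dropout in one arm: bias.** Suppose Arm A loses 20%, with log-odds of dropout linear in month-3 CNC, and Arm B loses 20% at random. The completers-only bias is ρ × k, where k is the mean standardised month-3 score of Arm A completers.

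| Dropout odds per SD lower | k | ρ = 0.7 | ρ = 0.9 |
|---|---|---|---|
| 1.6-fold | 0.096 | 0.07 SD | 0.09 SD |
| 2.7-fold | 0.173 | 0.12 SD | 0.16 SD |
| 7.4-fold | 0.262 | 0.18 SD | 0.24 SD |

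Simulation with 30 per arm gives 0.065 to 0.236 SD, and at most about 0.01 SD once the month-3 score is modelled. If half the losses come before month 3 and are random, the range is about 0.04 to 0.14 SD. As a bound, if the lost 20% are exactly the lowest month-3 scorers, k = 0.280/0.8 = 0.35 and the bias is 0.24 to 0.31 SD. If the informative arm is B instead, the sign reverses.

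**5. SSQ12 as the SAP is written.** The listed imputation covariates omit treatment arm. With random dropout, imputed subjects in both arms then get about the same mean, so a true difference of 3.0 is estimated as about 0.8 × 3.0 = 2.4. With the Arm A dropout patterns of step 4 and a correlation of 0.3 to 0.7 between month-3 CNC and SSQ12, simulation gives about 2.4 to 2.7. Adding month-3 CNC without arm does not cure this: estimates run from about 2.35 to 2.86, taking an arm difference in month-3 CNC of 0 or 1.5 SD. With arm and month-3 CNC together the estimate returns to about 3.0.

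**The case against.** Several counter-arguments stand, and they limit the point.

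- **Direction.** A reader might infer that the plan overstates implant benefit, since before FUV1 only Arm A can leave because of a poor implant result. The documents do not support that. Arm B subjects are implant candidates asked to wait six months, and those doing worst with hearing aids also have a reason to leave. That bias runs the other way and could cancel or reverse the first.
- **SSQ12.** A reader might extend the overstatement to the primary endpoint. As SAP 6.4 is written the error is toward zero (step 5). An overstatement of 0.04 to 0.32 points arises only if arm is assumed to be in the imputation, and it is not listed.
- **Arm B's score.** The Arm B text also says implanted ear, so a reader might take both scores as post-activation. Arm B is implanted only after FUV1.
- **Circularity.** The near-complete correction in step 4 follows from generating dropout from month-3 CNC alone. Other causes of dropout would be corrected only in part.
- **Inputs.** The correlation is not documented. With the stated windows (surgery at 0 to 2 weeks, activation up to 5 weeks later, review at 9 to 17 weeks), Arm A's implant use at the test could range from about 2 to 17 weeks, which may weaken it. Step 4 also leaves out baseline, which the SAP already uses for SSQ12 and which would take up part of the gain there.
- **Status.** The test is labelled an audibility review, and SAP 6.7 says ancillary analyses carry no formal testing. Leaving it out is defensible. Even so, 6.7.1.1 attaches a 0.01 level to the CNC comparison, so its estimate will be read as a controlled result.

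**Conclusion.** The point holds as an optional, low-cost improvement. The three-month single-ear CNC score is collected in both arms and no SAP analysis reads it. The CNC A6 vs B6 comparison therefore rests on available cases when a strong predictor of the missing value may be on file.

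Under the assumptions of step 4, the potential bias is about 0.07 to 0.24 SD, or roughly half that if only half the losses follow month 3. The direction depends on which arm's dropout is informative. If dropout is random, the gain is precision only: 5 to 16% less variance. The 20% attrition is the SAP's figure and 30 per arm follows from its approximate total of 60; the correlations, dropout slopes and timing of losses are assumed. For SSQ12 the benefit is secondary, and it appears only if treatment arm is also in the imputation model.

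**What to change.** 1. **SAP 6.1.2:** add an A3/B3 time point for single-ear CNC words.
2. **SAP 6.7.1.1:** state that the CNC A6 vs B6 contrast is for the implanted ear (Arm A) or ear to be implanted (Arm B). At present no listening condition is named, and only the single ear is tested at month 3. Estimate it from a repeated-measures model of the month-3 and FUV1 scores, with arm, visit, arm-by-visit and baseline CNC and an unstructured covariance. Include all randomised subjects with any post-baseline score, and report the FUV1 contrast at the same 0.01 level. This also replaces the pairwise correlations, which do not compare means.
3. **SAP 6.4:** add month-3 CNC as an auxiliary variable in the SSQ12 imputation, in a model that also contains treatment arm.
4. **Protocol:** reconcile the implanted-ear wording for Arm B in 9.3.8.2.1 with section 5 and 9.3.9. Reconcile also the three-month window, which is 4 weeks either side in 9.3.8 and 2 weeks either side in section 5 and 9.2.3.1.2.

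The cost is SAP wording and a little programming before analysis, with no new visit, test or patient. The imputation model becomes slightly larger, and subjects lost before month 3 gain nothing.

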9.3.8.2 Hearing aid review – Arm B

Over the course of the hearing aid intervention, the subjects will be followed for hearing aid checks including verification of fitting, be counselled on hearing and listening strategies, and discuss hearing

assistive technology. Four to six clinical review visits will be scheduled at each field site between FUV1 and six (6) months from POV2.

We propose the following topics are discussed during the six months of the hearing aid intervention:

- Hearing assistive technology
- Communication strategies
- Listening in noise
- Understanding hearing loss

Needs for various hearing assistive technologies (HATs) will be assessed and, if the audiologist deems that it is appropriate, recommendations will be made.

Following each hearing aid fitting and follow up session an anonymized program settings file will be provided to the study sponsor in order to evaluate program settings and usage data.

9.3.8.2.1 Audibility Review – three months post POV2.

As part of the clinical review visits, at three (3) months (+/- 4 weeks) post POV2, audibility will be assessed.

- Implanted ear only: Aided speech recognition with CNC words at 60 dBA (2 lists)
- Everyday listening condition (bilateral hearing aids): Sound field thresholds at 500, 1000, 2000, 4000 Hz

9.3.9 Follow-up Visit 1 (FUV1)

Both Arm A and Arm B subjects will complete FUV1 in the aided condition six (6) months post POV2 (+/- 2 weeks). The full neuropsychological battery in addition to the audiologic, psychosocial, physical, and quality of life metrics will be completed as described in Section 9.2. Speech recognition will be assessed in the everyday listening condition (aided bilaterally) and implanted ear (Arm A) or ear to be implanted (Arm B) only listening conditions. Datalogs will be retrieved for the sound processor (Arm A) and hearing aid (Arm B).

9.3.10 Surgery – Arm B

Arm B subjects will be implanted with the Cochlear Nucleus® Profile™ Slim Modiolar (532) cochlear implant or the Cochlear Nucleus CI632 cochlear implant 1 week (+/- 1 week) post FUV1.

An intraoperative X-ray will be obtained (preferably a lateral or modified Stenver's view) following the placement of the electrode and prior to closing.

9.3.11 Imaging

Following surgery, subjects will undergo a Computed Tomography (CT) scan according to the specifications provided by the study sponsor. Postoperative analysis of the CT scan will be done via reconstruction to determine electrode position and distance to the modiolus. Retrospective analysis of the CT scan will be done via reconstruction to determine electrode position and distance to the modiolus by an independent centralized imaging review center and a de-identified report will be sent to the sponsor in line with HIPAA Standards.

9.3.12 CI review – Arm B

CI activation will occur in the standard clinical manner for each field site at approximately two weeks post-surgery (+/- 3 weeks). Four to six clinical review visits will be scheduled at each field site between activation and FUV2, twelve (12) months from POV2. These visits can contain device

adjustments as well as counselling on hearing and listening strategies, and discussion of hearing assistive technology.

We propose the following topics are discussed during the six months of cochlear implant use:

- Hearing assistive technology
- Communication strategies
- Listening in noise
- Understanding hearing loss

Needs for various hearing assistive technologies (HATs) will be assessed and, if the audiologist deems that it is appropriate, recommendations will be made.

Following each CI mapping appointment an anonymized .cdx file labelled with the Subject ID will be provided to the study sponsor in order to evaluate program settings and usage data.

9.3.13 Follow-up Visit 2 (FUV2)

Both Arm A and Arm B subjects will complete FUV2 in the aided condition twelve (12) months post POV2 (+/- 4 weeks). The full neuropsychological battery in addition to the audiologic, psychosocial, physical, and quality of life metrics will be completed as described in Section 9.2. Speech recognition will be assessed in the everyday listening condition (aided bilaterally) and implanted ear only listening condition. Datalogs will be retrieved for the sound processor.

9.3.14 Follow-up Visit 3 (FUV3)

Arm B subjects will complete FUV3 in the aided condition eighteen (18) months post POV2 (+/- 4 weeks). The full neuropsychological battery in addition to the audiologic, psychosocial, physical, and quality of life metrics will be completed as described in Section 9.2. Speech recognition will be assessed in the everyday listening condition (aided bilaterally) and implanted ear only listening condition. Datalogs will be retrieved for the sound processor.

9.4 Subjects

9.4.1 Inclusion Criteria

1. Aged 65 to 85 years, inclusive
2. Community-dwelling
3. Proficient in English
4. Oral communicator
5. PTA (500, 1000 & 2000 Hz) \geq 70 dB HL hearing loss duration \geq 1 year and no more than 30 years.
6. Active hearing aid users: daily use of hearing aids.
7. Hearing Handicap Inventory for the Elderly - Screening (HHIE-S): Score \geq 24 indicating a significant hearing handicap
8. Hearing Impaired Montreal Cognitive Assessment (HI-MoCA): Score \geq 20 indicating mild cognitive decline to normal cognitive function.
9. Cochlear implant candidacy: Participants must have postlinguistic onset sensorineural hearing loss and meet applicable FDA and/or Medicare candidacy criteria for cochlear implantation

10. Willingness to consent for the study, to be randomized to either the immediate or delayed cochlear implantation arm, to utilize bimodal hearing for the duration of the trial (if clinically appropriate) and follow the study protocol for the duration of the trial.

9.4.2 Exclusion Criteria

1. Prelingual or perilingual severe-to-profound hearing loss.
2. Previous cochlear implantation in either ear
3. Hearing loss of neural or central origin
4. Permanent conductive hearing impairment (e.g. Otosclerosis).
5. Medical, audiological or psychological conditions, as judged by the investigator that might contraindicate participation in the clinical investigation.
6. Self-reported disability in ≥ 2 activities of daily living.
7. Unwilling to wear a device or comply with the surgical and rehabilitation requirements of the study.
8. Vision impairment: Worse than 20/40 (corrected) on a Near Vision Card.

9.5 Statistical Considerations

Statistical considerations for the clinical investigation are fully described within the Randomized controlled trial of immediate versus delayed cochlear implantation Statistical Analysis Plan (D1309522).

9.6 Data Management

The Case Report Forms (CRFs) will capture subject status according to the following criteria:

- Consented: Signed consent and eligibility evaluations underway
- Screen Fail: Subject determined not to be eligible to proceed for participation
- Enrolled: Following confirmation of eligibility and randomization
- Withdrawn: Enrolled subjects who withdraw or are withdrawn by the Investigator or Sponsor before the expected End of Study visit.
- Complete: Enrolled subjects who complete the planned follow up schedule.

Source data collection will be performed through Medidata Rave, a web-based system for electronic data capturing (EDC). Site personnel will be trained to use this system. Data validity has to be confirmed by the investigator through an electronic signature. An audit trail is kept by this system and data clarifications may be generated by the system and sponsor personnel after review of data.

The web-based system has been verified and validated by the vendor. Investigation-specific implementations are validated and consist of verification that all required items are included, validity of edit checks and appropriate functionality of conditional fields. The investigation-specific data in the EDC can only be accessed by those that have been allocated their individual account, which are personnel of the investigational sites, Clinical Project Managers, Investigation Monitors and Data Management.

